24.3 Definition of Evaluable Participant

In Module 2, Part A, an evaluable participant is any participant who received a dose of study drug.

24.4 Duration of Therapy

Participants will move from AZD4573 monotherapy to combination treatment (AZD4573 + acalabrutinib) based on the Lugano overall response ([Table 36](#)) ([Cheson et al 2014](#)).

Table 29 **Part A - Duration of AZD4573 Monotherapy**

Disease Assessment	Lugano 2014 Overall Response	Treatment	Next Scheduled Disease Assessment
Period 1, Cycle 2, Week 3 ^a	CR	Continue AZD4573 monotherapy (Period 1, Cycle 3)	Period 1, at Cycle 5, Week 3
	PR	Continue AZD4573 monotherapy (Period 1, Cycle 3)	Period 1, at Cycle 5, Week 3
	SD	Continue AZD4573 monotherapy (Period 1, Cycle 3) ^b	Period 1, at Cycle 5, Week 3
	PD	Start combination therapy (Period 2, Cycle 1)	Period 2, after 2 cycles (Section 26.4.2)
Period 1, Cycle 5, Week 3 ^a	CR	Continue AZD4573 monotherapy (Period 1, Cycle 6)	Period 1, after 8 cycles (Section 26.4.2)
	PR	Continue AZD4573 monotherapy (Period 1, Cycle 6) ^b	Period 1, after 8 cycles (Section 26.4.2)
	SD	Start combination therapy (Period 2, Cycle 1)	Period 2, after 2 cycles (Section 26.4.2)
	PD	Start combination therapy (Period 2, Cycle 1)	Period 2, after 2 cycles (Section 26.4.2)

^a Schedule the disease assessment to ensure availability of Lugano overall response ([Cheson et al 2014](#)) before Day 1 of the subsequent cycle.

^b AZD4573 + acalabrutinib combination treatment (Period 2, Cycle 1) can be started at the discretion of the investigator.

Note: AZD4573 + acalabrutinib combination treatment (Part A, Period 2) shall be started, if the participant develops PD at any time during the AZD4573 monotherapy (Part A, Period 1).

Abbreviations: CR = complete response; PD = progressive disease; PR = partial response; SD = stable disease.

24.5 Preparation/Handling/Storage/Accountability of Interventions

Please refer to Section [6.8](#) for general instructions and instructions specific to AZD4573.

Acalabrutinib drug accountability

Participant reported drug administration for acalabrutinib needs to be done on every AZD4573 dosing day, ideally prior to dosing (\pm 24 hours) and is also to be done after the last acalabrutinib capsule is taken and the leftover capsules returned to site. Drug accountability for acalabrutinib will occur every two weeks (on an AZD4573 dosing day, ideally prior to dosing [\pm 24 hours]).

The returned number of acalabrutinib capsules needs to be counted and the participant will be asked whether or not acalabrutinib was taken according to the instructed dosing schedule.

Deviations from the instructed schedule should be discussed with the participant and recorded both in the source documents and the eCRF.

Discrepancies between the expected and returned number of capsules should be discussed with the participant and recorded in the source documents.

24.6 Measures to Minimise Bias: Randomisation and Blinding

This is an open-label, non-randomised study (please refer to Section [6.9](#)).

24.7 Study Intervention Compliance

AZD4573

Participants are dosed at the site, they will receive study intervention directly from the Investigator or designee, under medical supervision. The date, and time if applicable, of dose administered in the clinic will be recorded in the source documents and recorded in the eCRF. The dose of study intervention and study participant identification will be confirmed at the time of dosing by a member of the study-site staff other than the person administering the study intervention.

Acalabrutinib

Acalabrutinib drug accountability will be conducted as described in Section [24.5](#) and this will be recorded by the site. If the participant made an error or dropped/lost capsules the site will need to check that the participant will have sufficient capsules for the following week. Deviation(s) from the prescribed dosage regimen should be recorded in the eCRF.

A record of the number of acalabrutinib capsules dispensed to and taken by each participant must be maintained and reconciled with study intervention and compliance records.

Intervention start and stop dates, including dates for intervention delays and/or dose reductions will also be recorded in the eCRF.

24.8 Concomitant Therapy

The Investigator must be informed as soon as possible about any concomitant medication taken from the time of screening until the end of the clinical phase of the study (final study visit). Any concomitant therapy(ies), including over-the-counter medications, herbal remedies, vaccines, and supplements, taken during the study will be recorded.

24.8.1 Permitted Concomitant Therapy

Investigators may prescribe concomitant medications or treatments deemed necessary to provide adequate supportive care except for those medications identified as “excluded” as listed in Section [24.8.2](#). Specifically, participants should receive full supportive care during

the study and treatment with antibiotics, anti-emetics, antidiarrheals, and analgesics, and other care as deemed appropriate, and in accordance with their institutional guidelines.

After the start of AZD4573 and acalabrutinib administration, blood and platelet transfusions are allowed as clinically indicated at any time during the study and can be given as per local institutional guidelines.

Supportive care (eg, recombinant growth factor support) and other medications that are considered necessary for the participant's wellbeing, (eg, bisphosphonates), may be given at the discretion of the Investigator and in accordance with local institutional guidelines.

Concomitant use of paracetamol is permitted but is limited to a maximum dose of 4 grams per day.

AstraZeneca recommends administering non-live inactivated vaccines 72 hours prior to administration of the first dose of any IP to avoid biases in the interpretation of safety data due to the potential overlap of vaccine-related AEs with IP AEs.

Permitted concomitant therapy for the management of safety concerns for AZD4573 and acalabrutinib (including TLS) is specified in Section 26.1.10. For guidance on additional prophylaxis for TLS, see Section 26.1.10.10. Administer appropriate hydration and allopurinol or rasburicase per institutional standards before initiating treatment.

24.8.2 Prohibited Concomitant Therapy

Participants must be instructed not to take any medications, including over-the-counter products, herbal remedies, and supplements without first consulting with the Investigator.

The following medications are considered exclusionary during the study. AstraZeneca must be notified if a participant receives any of these during the study:

- Any investigational anti-cancer therapy.
- Any concurrent chemotherapy, radiotherapy (except palliative radiotherapy), immunotherapy, biologic, or hormonal therapy for cancer treatment. Concurrent use of hormones for noncancer-related conditions (eg, insulin for diabetes and hormone replacement therapy) is acceptable.
- Participants may use topical or inhaled corticosteroids as therapy for comorbid conditions. Ongoing use of low-dose systemic corticosteroids (≤ 10 mg/day prednisolone or equivalent) is permitted (Section 6.11).
- Warfarin or equivalent vitamin K antagonists (eg, phenprocoumon) are prohibited for all participants in the study. Participants who require anticoagulation prophylaxis before

study treatment start or therapeutic anticoagulation for thrombosis while on study will be allowed to receive anticoagulation with a non-vitamin K inhibitor class of anticoagulants. Should participants require either a vitamin K antagonist or combined administration of antiplatelet and therapeutic anticoagulation while on study, acalabrutinib treatment must be discontinued.

For further restrictions on the concomitant use of therapies and possible drug-drug interactions with AZD4573 and acalabrutinib, please refer to Section [6.11](#) and Section [24.8.4](#), respectively.

24.8.3 AZD4573 and Concomitant Therapy

For further specific information on AZD4573 and concomitant therapy, please refer to Section [6.11](#).

24.8.4 Acalabrutinib and Concomitant Treatments

The effect of agents that reduce gastric acidity (antacids or proton-pump inhibitors) on acalabrutinib absorption was evaluated in a healthy volunteer study (ACE-HV-004). Results from this study indicate that participants should avoid the use of calcium carbonate containing drugs or supplements for a period of at least 2 hours before and at least 2 hours after taking acalabrutinib. Use of omeprazole, esomeprazole, lansoprazole, or any other proton-pump inhibitors while taking acalabrutinib is not recommended due to a potential decrease in study treatment exposure. However, the decision to treat with proton-pump inhibitors during the study is at the Investigator's discretion, with an understanding of the potential benefit to the participant's gastrointestinal condition and a potential risk of decreased exposure to acalabrutinib. Although the effect of H₂-receptor antagonists (such as famotidine or ranitidine) on acalabrutinib absorption has not been evaluated, if treatment with an H₂-receptor antagonist is required, the H₂-receptor antagonist should be taken approximately 10 hours before or 2 hours after acalabrutinib.

Acalabrutinib is not a strong direct inhibitor or inducer of CYP isoforms; thus, acalabrutinib, at the currently used clinical doses, is unlikely to be a perpetrator of a drug-drug interaction at the level of inhibition or induction of CYP isoforms. The concomitant use of strong inhibitors/inducers of CYP3A should be avoided (please refer to [Appendix F](#)). Because acalabrutinib is metabolised by CYP3A, participants should be strongly cautioned against consumption of grapefruit, grapefruit juice, or Seville orange juice (which contain potent CYP3A inhibitors) or using herbal remedies or dietary supplements (in particular, St. John's wort, which is a potent CYP3A inducer). If a participant requires short-term treatment with a strong CYP3A inhibitor (such as anti-infectives for up to 7 days), interrupt acalabrutinib treatment. From Cycle 2 onwards, if a participant requires a moderate CYP3A inhibitor while on study, decrease acalabrutinib dose to 100 mg once daily. Avoid co-administration of strong

CYP3A inducers. If a participant requires treatment with a strong CYP3A inducer, increase the acalabrutinib dose to 200 mg twice daily during concomitant administration with the strong CYP3A inducer and return to recommended dose of 100 mg twice daily after stopping the strong CYP3A inducer.

Concomitant use of paracetamol is permitted but is limited to a maximum dose of 4 grams per day. For participants dosed with AZD4573 and acalabrutinib non-steroidal anti-inflammatory agents such as ibuprofen should also be avoided.

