24.1 Study Intervention(s) Administered

24.1.1 Investigational Products

AZD4573 will be administered as an absolute (flat) dose, 2-hour (\pm 15 minutes) IV infusion once weekly, at least 5 days apart, alone and in combination with acalabrutinib 100 mg twice daily continuously.

AZD4573 and acalabrutinib will be supplied by AstraZeneca. CC1

Detailed

information on the drug products and administration guidelines are in the AZD4573 Handling Instructions and acalabrutinib participant leaflet.

Table 28 Investigational Products

Intervention Name	AZD4573	Acalabrutinib
Type	Drug	Drug
Dose Formulation	Concentrate for solution for infusion	Capsules
Unit Dose Strength(s)	1.5 mg/mL	100 mg
Dose	Part A Period 1: 12 mg* Part A Period 2: dose to be established based on emerging data from Module 1	100 mg BID
Route of Administration	IV infusion	Oral
Use	Experimental	Experimental
IMP and NIMP	IMP	IMP

Intervention Name	AZD4573	Acalabrutinib
Sourcing	Provided centrally by AstraZeneca	Provided centrally by AstraZeneca
Packaging and Labelling	Study Intervention will be provided in vials. Each vial will be labelled as required per country requirement	Study Intervention will be provided in bottles. Each bottle will be labelled as required per country requirement
Current/Former Name(s) or Alias(es)	AZD4573/ AZ13810325	Acalabrutinib/ACP-196 /Calquence

*In Period 1, target dose of 12 mg achieved through intra-patient ramp up from starting dose on Day 1 (6 mg), with subsequent titration to the intermediate dose on Day 8 (9 mg), and to target dose of 12 mg on Day 15.

Abbreviations: BID = twice daily; IMP = investigational medicinal product; IV = intravenous;
NIMP = non-investigational medicinal product.

Labels will be prepared in accordance with Good Manufacturing Practice and local regulatory guidelines and will be translated into the local language. The labels will fulfil Good Manufacturing Practice Annex 13 requirements for labelling.

All IPs should be kept in a secure place under appropriate storage conditions. The IP label on the vial (AZD4573) or bottle (acalabrutinib) specifies the appropriate storage conditions.

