26.3 Overdose

Please refer to Section 8.3 for general information and information related to AZD4573.

An acalabrutinib overdose is defined as any dose that is higher than the investigated dose. For any participant experiencing an acalabrutinib overdose, observation for any symptomatic side effects should be instituted, and vital signs, biochemical and haematological parameters should be followed closely (consistent with the protocol or more frequently, as needed). Appropriate supportive management to mitigate adverse effects should be initiated. If the overdose ingestion of acalabrutinib is recent and substantial, and if there are no medical contraindications, use of gastric lavage or induction of emesis may be considered.

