Appendix G Strong Inhibitors and Inducers of CYP3A

Avoid co-administration of these agents with acalabrutinib, if possible. If not possible to avoid, monitor for toxicity (with inhibitors of CYP3A) and potential reduction in efficacy (with CYP3A inducers).

Strong Inhibitors of CYP3A ^a	Strong Inducers of CYP3A ^e
boceprevir	apalutamide
cobicistat ^b	carbamazepine ^f
clarithromycin ^b	enzalutamide
danoprevir and ritonavir ^c	mitotane
elvitegravir and ritonavir ^c	phenytoin ^f
grapefruit juice ^d	rifampin ^f
idelalisib	St John's wort ^f
indinavir and ritonavir ^c	
itraconazole ^b	
ketoconazole	
lopinavir and ritonavir ^{b,c}	
paritaprevir and ritonavir and (ombitasvir and/or dasabuvir) ^c	
nefazodone	
nelfinavir	
posaconazole	
ritonavir ^{b,c}	
saquinavir and ritonavir ^c	
telaprevir	
tipranavir and ritonavir ^c	
telithromycin	
troleandomycin	
voriconazole	

^a A strong inhibitor for CYP3A is defined as an inhibitor that increases the area under the concentration-time curve (AUC) of a substrate for CYP3A by ≥ 5 -fold.

^b In vivo inhibitor of P-glycoprotein.

^c Ritonavir is usually given in combination with other anti-HIV or anti-HCV drugs in clinical practice. Caution should be used when extrapolating the observed effect of ritonavir alone to the effect of combination regimens on CYP3A activities.

^d The effect of grapefruit juice varies widely among brands and is concentration-, dose-, and preparation-dependent. Studies have shown that it can be classified as a “strong CYP3A inhibitor” when a certain preparation was used (eg, high dose, double strength) or as a “moderate CYP3A inhibitor” when another preparation was used (eg, low-dose, single strength).

^e A strong inducer for CYP3A is defined as an inducer that results in $\geq 80\%$ decrease in the AUC of a substrate for CYP3A.

f In vivo inducer of P-glycoprotein.

Note: The list of drugs in this table is not exhaustive. Any questions about drugs not on this list should be addressed to the Medical Monitor of the protocol.

Source: FDA Drug Development and Drug Interactions: Table of Substrates, Inhibitors, and Inducers.
<http://www.fda.gov/Drugs/DevelopmentApprovalProcess/DevelopmentResources/DrugInteractionLabeling/ucm093664.htm#inVivo> (Accessed 05 April 2020).

Appendix H Changes Related to Mitigation of Study Disruptions Due to Cases of Civil Crisis, Natural Disaster, or Public Health Crisis

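### Appendix G offers only monitoring when a strong CYP3A agent cannot be avoided, and does not refer back to the acalabrutinib actions that Section 24.8.4 orders

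*Protocol*

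**What the plan says.** Section 24.8.2 directs the reader onward: "For further restrictions on the concomitant use of therapies and possible drug-drug interactions with AZD4573 and acalabrutinib" are to be found in 6.11 and 24.8.4 respectively, so 24.8.4 is the governing section for acalabrutinib.

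Section 24.8.4 says that strong CYP3A inhibitors and inducers should be avoided, and then says what to do if one is needed:

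- Strong inhibitor: "If a participant requires short-term treatment with a strong CYP3A inhibitor (such as anti-infectives for up to 7 days), interrupt acalabrutinib treatment".
- Strong inducer: "increase the acalabrutinib dose to 200 mg twice daily during concomitant administration with the strong CYP3A inducer", with a return to 100 mg twice daily afterwards.
- Moderate inhibitor, from Cycle 2 onwards: acalabrutinib is reduced to 100 mg once daily.

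Appendix G lists the strong agents. Its header begins "Avoid co-administration of these agents with acalabrutinib, if possible" and continues "If not possible to avoid, monitor for toxicity (with inhibitors of CYP3A) and potential reduction in efficacy (with CYP3A inducers". It gives no dose and no reference to 24.8.4. Its footnote a reads "A strong inhibitor for CYP3A is defined as an inhibitor that increases the area under the concentration-time curve (AUC) of a substrate for CYP3A", with a threshold of at least 5-fold.

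Section 23.2 (criterion 5) and Section 24.8.4 both cite Appendix F for this list. Appendix F contains the tumour lysis syndrome definitions.

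Section 26.3 states: "An acalabrutinib overdose is defined as any dose that is higher than the investigated dose". The Module 2 regimen in 24.1.1 is AZD4573 "alone and in combination with acalabrutinib 100 mg twice daily continuously".

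**The concern.** The section text and the appendix address the same situation, a strong CYP3A agent that the participant needs, and they give different amounts of instruction. Monitoring for toxicity most naturally presumes that acalabrutinib is still being taken, whereas 24.8.4 stops it. A site that starts from the drug list sees no sign that anything more is required. A site that starts from 24.8.4 is sent to the wrong appendix for the list.

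The situation is foreseeable. Criterion 5 screens out need at entry only. Section 26.1.10.8 says that anti-fungal prophylaxis should follow institutional guidelines and carries no CYP3A caveat there, and Appendix G lists itraconazole, ketoconazole, posaconazole and voriconazole as strong inhibitors. Either choice has a cost. Continuing risks excess exposure, while the note to Table 30 in Section 24.9 warns that withholding acalabrutinib for as little as 7 days can transiently worsen mantle cell lymphoma. Sites should not have to infer which course the protocol intends.

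A smaller point follows for inducers: the dose that 24.8.4 orders is above the standard Module 2 dose, and 26.3 makes no allowance for it.

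**Working it through.** There is no planned figure to reproduce. The check compares the texts and adds simple dose arithmetic.

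| Situation on study | Section 24.8.4 | Appendix G header | Relation |
|---|---|---|---|
| Short-term strong inhibitor required | Interrupt acalabrutinib (0 mg/day) | Monitor for toxicity; no dose stated | Ambiguous: monitoring suggests that dosing continues |
| Strong inhibitor needed for longer | General advice to avoid; no action on acalabrutinib | Monitor for toxicity | Only the header speaks to this case |
| Strong inducer required | 200 mg twice daily, then back to 100 mg twice daily | Monitor for loss of efficacy; no dose stated | Compatible, but the dose is missing |
| Moderate inhibitor, from Cycle 2 | 100 mg once daily | Not covered | No overlap |

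The first and last rows show the oddity. Read alone, the header asks for less action with a strong inhibitor (monitoring) than 24.8.4 asks for with a moderate one (half the daily dose).

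**Dose arithmetic**

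- Standard dose (24.1.1): 100 mg × 2 = 200 mg/day.
- With a strong inducer (24.8.4): 200 mg × 2 = 400 mg/day.
- Ratio: 400 / 200 = 2.0.

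If the investigated dose in 26.3 means the standard 100 mg twice daily, the ordered dose exceeds it and meets the definition as worded.

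**Illustration of exposure with an inducer.** The document gives no acalabrutinib-specific figure. Assume that the inducer lowers acalabrutinib AUC by a fraction d, with d between 0.50 and 0.80; Appendix G uses an 80% fall in substrate AUC as its threshold for a strong inducer. Relative exposure = 2.0 × (1 − d).

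- d = 0.50: 2.0 × 0.50 = 1.0 times usual.
- d = 0.80: 2.0 × 0.20 = 0.4 times usual.

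Over this assumed range the ordered dose gives no more than usual exposure, so an overdose label would not describe what the participant receives.

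**Reach.** Section 27.2 plans approximately 12 participants in Module 2. Section 18.5 records that enrolment is permanently halted. Section 23.6 lets participants who are still benefiting continue treatment after the primary analysis, so dosing instructions can still apply, but the number still on acalabrutinib is not given.

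**The case against.** The strongest reply is that nothing here conflicts. Section 24.8.4 is specific, 24.8.2 names it as the governing section, and an appendix list need not repeat it. Interrupting acalabrutinib is itself a way to avoid co-administration, and monitoring efficacy sits comfortably beside a dose increase. The header may also serve cases that 24.8.4 leaves open, such as longer inhibitor use. Appendix G is not labelled for one module, and the corresponding Module 1 and core texts are not shown, so the absence of Module 2 doses is unsurprising.

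Much of this stands. A reader might infer a flat contradiction between 24.8.4 and Appendix G. The documents do not support that, because the two can be reconciled. What remains is that the reconciliation is left to the site: the header describes the unavoidable case without the ordered action, carries no reference back, and is reached through a wrong cross-reference.

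A reader might also infer that the protocol classes its own ordered dose as an overdose. That goes too far. Section 26.3 does not define the investigated dose, a dose that the protocol directs can fairly be read as part of the investigated regimen, and 26.3 refers to Section 8.3, which is not shown and may settle the matter. Even on the literal reading, the main consequence is observation and closer follow-up.

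Finally, the 5-fold figure is a general definition for CYP3A substrates, not a measured effect on acalabrutinib. Anti-fungal prophylaxis may also run beyond the short-term use that 24.8.4 addresses.

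**Conclusion.** The point holds as a minor patient-safety inconsistency in the drafting, not as a fault in the choice of design. For a required short-term strong inhibitor, a site that follows the Appendix G header as written could continue acalabrutinib when 24.8.4 says to stop it. For a strong inducer the header omits a dose adjustment with which it is otherwise compatible. The two references to Appendix F are plain errors. The 26.3 wording is a secondary clarification that depends on what Section 8.3 says.

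The size is small: about 12 planned participants, no further enrolment, and an entry criterion that excludes anyone who already requires these agents. The document does not show that any participant was dosed wrongly or that a strong inducer was ever used. No endpoint, sample size or analysis changes. It is still worth correcting, because it concerns dosing of individual participants and costs almost nothing.

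**What to change.** 1. Keep both existing sentences of the Appendix G header and add: *For Module 2 follow Section 24.8.4: interrupt acalabrutinib during a required short-term strong CYP3A inhibitor; give 200 mg twice daily during a required strong CYP3A inducer and return to 100 mg twice daily afterwards.*
2. Change Appendix F to Appendix G in Section 23.2, criterion 5, and in Section 24.8.4.
3. As a secondary clarification, once checked against Section 8.3, add to 26.3: *A dose of 200 mg twice daily given as directed in Section 24.8.4 is not an overdose.*

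The cost is two added sentences and two corrected references, with no change to dosing rules, visits, data collection or analysis. These edits only align the texts. They do not supply an action for strong inhibitors used for longer than 7 days, including extended azole prophylaxis; that would need a separate clinical decision by the sponsor.
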